### 7.5.2.5 Other Secondary Analyses

The rates of hospitalization for respiratory ailments, which is defined as the number of patients with any hospitalization for respiratory ailments divided by the total study duration (years) summed over patients in that treatment arm and then multiplied by 100 to present in terms of per 100 patient years, will be tabulated by treatment arm. Tests of differences in event rate will be assessed using chi-squared tests ( $\chi^2$ ) at the 2-sided, 0.05 level of significance. Corresponding exact 95% CIs of study treatment proportions and respective active ND-L02-s0201 differences from placebo will be estimated. Time to hospitalization for respiratory ailments or death is defined as the time from start of study treatment to hospitalization for respiratory ailments or death for each subject. Subjects who do not experience hospitalization for respiratory ailments and have not died will be censored to last known alive date. The analysis of time to hospitalization for respiratory ailments or death of each active treatment arm versus placebo will be performed using a log-rank test stratified with standard of care to generate p-value for each comparison. Median time to hospitalization for respiratory ailments or death and corresponding 95% CI as well as proportion of subjects without the event at the 8- week interval will be summarized for each treatment arm using the Kaplan-Meier (KM) analysis. KM plot of time to hospitalization for respiratory ailments or death will also be presented by treatment. The hazard ratio and 95% CI will be calculated from a stratified Cox proportional hazards model that including standard of care as the strata.

Rate of mortality due to any cause, which is defined as the number of patients who died due to any cause, divided by the total study duration (years) summed over patients in that treatment arm and then multiplied by 100 to present in terms of per 100 patient years, will be analyzed similarly as the rate of hospitalization for respiratory ailments. In addition, overall survival which is defined as the time from start of study treatment to death due to any cause will be analyzed similarly as time to hospitalization for respiratory ailments. Any patient not known to have died at the time of analysis will be censored to the last known alive date.

Rate of deterioration of IPF resulting in lung transplantation (up to 12 weeks after the end of study treatment) or death, which is defined as the number of patients with

## Statistical Analysis Plan

Sponsor Name: Nitto Denko Corporation  
Sponsor Protocol ID: ND-L02-s0201-005

any deterioration of IPF resulting in lung transplantation divided by the total study duration (years) summed over patients in that treatment arm and then multiplied by 100 to present in terms of per 100 patient years, will be analyzed similarly as the rate of hospitalization for respiratory ailments. In addition, time to deterioration of IPF resulting in lung transplantation or death defined as the time from start of study treatment to deterioration of IPF resulting in lung transplantation (up to 12 weeks after the end of study treatment) or death will be analyzed similarly as time to hospitalization for respiratory ailments. Any patient not known to have IPF resulting in lung transplantation (up to 12 weeks after the end of study treatment) or death at the time of analysis will be censored to 12 weeks after the end of study treatment or the last known alive date, whichever is earlier.

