#### 13.1.2. Secondary Endpoint

##### 13.1.2.1. Biological Activity

- Rate of decline in FVC over 24 weeks (measured in mL and % of predicted over unit time)
- Absolute and relative change in FVC (mL and % of predicted) at Visit 14 (Day 169) as compared with baseline
- Proportion of subjects with an FVC response (mL and % of predicted) defined as either having improvement or a decline by 0% to  $\leq 5\%$ ,  $> 5\%$  to  $\leq 10\%$ , and by  $> 10\%$  at Visit 14 (Day 169)
- Change in DLCO and DLCO corrected for hemoglobin
- Changes of ILA as measured by HRCT (ie, change in parenchymal feature [Baseline to Visit 14 (Day 169)]), as determined by qualitative assessment (central radiologist) and quantitative analysis (Quantitative Lung Fibrosis – QLF analysis)
- Time to first acute IPF exacerbation (ie, an unexplained worsening of dyspnea, evidence of hypoxemia as defined by worsened or severely impaired gas exchange, new radiographic alveolar infiltrates, and an absence of an alternative explanation such as infection, pulmonary embolism, pneumothorax, or heart failure [Raghu et al, 2011])

- Rate of hospitalization for respiratory ailments, rate of mortality due to all causes, and rate of deterioration of IPF resulting in lung transplantation (up to 12 weeks after the end of study treatment) or death

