### 3.2 Secondary Endpoints

#### Biological Activity

## Statistical Analysis Plan

Sponsor Name: Nitto Denko Corporation  
Sponsor Protocol ID: ND-L02-s0201-005

- Rate of decline in FVC from baseline to Visit 14 (Day 169) (measured in L and % of predicted over unit time)
- Absolute and relative change in FVC (L and % of predicted) at Visit 14 (Day 169) as compared with baseline
- Proportion of subjects with an FVC response (L and % of predicted) defined as either having improvement or a decline by 0% to  $\leq 5\%$ ,  $> 5\%$  to  $\leq 10\%$ , and by  $> 10\%$  at Visit 14 (Day 169)
- Change in DLCO (mL/min/mmHg) and DLCO (mL/min/mmHg) corrected for hemoglobin at Visit 14 (Day 169)
- Changes of ILA as measured by HRCT (i.e., change in parenchymal feature [Baseline to Visit 14 (Day 169)]), as determined by qualitative assessment (central radiologist) and quantitative analysis (Quantitative Lung Fibrosis – QLF analysis)
- Time to first acute IPF exacerbation (i.e., an unexplained worsening of dyspnea, evidence of hypoxemia as defined by worsened or severely impaired gas exchange, new radiographic alveolar infiltrates, and an absence of an alternative explanation such as infection, pulmonary embolism, pneumothorax, or heart failure [Raghu et al, 2011]) or death
- Rate of hospitalization for respiratory ailments and time to first hospitalization for respiratory ailments or death
- Rate of mortality due to all causes and overall survival
- Rate of deterioration of IPF resulting in lung transplantation (up to 12 weeks after the end of study treatment) or death and time to deterioration of IPF resulting in lung transplantation (up to 12 weeks after the end of study treatment) or death

[REDACTED]

- [REDACTED]
- [REDACTED]
- [REDACTED]

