**CONFIDENTIAL**

## Statistical Analysis Plan

Sponsor Name: Nitto Denko Corporation  
Sponsor Protocol ID: ND-L02-s0201-005

The rate of acute IPF exacerbation, which is defined as the number of patients with any acute IPF exacerbation divided by the total study duration (years) summed over patients in that treatment arm and then multiplied by 100 to present in terms of per 100 patient years, will be summarized by treatment arm. Tests of differences in rates between treatment arms will be assessed using chi-squared tests ( $\chi^2$ ) at the 2-sided, 0.05 level of significance. Corresponding exact 95% CIs of study treatment proportions and respective active ND-L02-s0201 differences from placebo will be estimated.

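### The transplant-or-death rate in SAP Section 7.5.2.5 is defined with a numerator that leaves out deaths

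*SAP*

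**What the plan says.** The protocol lists the endpoint in Section 13.1.2.1 as "rate of deterioration of IPF resulting in lung transplantation (up to 12 weeks after the end of study treatment) or death". SAP Section 3.2 keeps that name and adds a time-to-event version: "Rate of deterioration of IPF resulting in lung transplantation (up to 12 weeks after the end of study treatment) or death and time" and so on.

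SAP Section 7.5.2.5 then defines the rate in one sentence that runs across a page break. The part before the break ends "or death, which is defined as the number of patients with". The part after it begins "any deterioration of IPF resulting in lung transplantation divided by the total study duration (years) summed over patients in that treatment arm", and the result is scaled to 100 patient-years. The rate is to be analysed like the respiratory hospitalisation rate, for which the SAP says: "Tests of differences in event rate will be assessed using chi-squared tests".

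The next sentence gives the time-to-event version, "time to deterioration of IPF resulting in lung transplantation or death defined as the time from start of study treatment", and there the event is transplantation or death. Patients without an event are censored at the earlier of 12 weeks after the end of treatment and the date last known alive.

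**The concern.** The name of the rate includes death and its definition does not. A programmer who follows the sentence as written will produce a table whose title promises a composite and whose content is transplants alone.

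This is not the SAP's usual pattern. For acute exacerbation and for respiratory hospitalisation, the SAP pairs an event-only rate with a time-to-event analysis that adds death, but those rates are also named as event-only. Here the rate's own name includes death.

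The missing component is probably the larger one. Protocol Section 8.2 excludes patients expected to receive a lung transplant during the study, so transplants should be rare. The rate could be close to zero in every arm while the Kaplan-Meier curve for the same named endpoint shows events.

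**Working it through.** **Comparison of the texts**

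| Place | Transplantation | Death |
|---|---|---|
| Protocol 13.1.2.1, rate | yes | yes |
| SAP 3.2, rate and time to event | yes | yes |
| SAP 7.5.2.5, name of the rate | yes | yes |
| SAP 7.5.2.5, numerator of the rate | yes | **no** |
| SAP 7.5.2.5, time to event | yes | yes |

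The two halves of the defining sentence join grammatically across the page header, with no redaction mark between them, so no text is missing. The visible part of SAP Section 8 (changes from the protocol) does not list removal of death from this rate. Other parts of that section are blacked out.

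**Size of the effect**

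Neither document gives an event rate or power figure for this endpoint, so there is no stated figure to reproduce. What follows is an illustration.

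- Arm size: 40 (SAP Section 2.3).
- Follow-up: Day 1 to Day 239 (Visit 16) = 238 days = 238/365.25 = 0.6516 years. It is assumed complete for every subject.
- Patient-years per arm: 40 × 0.6516 = 26.06.
- Formula: rate = 100 × patients with an event / patient-years.
- Assumed events: 0 transplants and 2, 3 or 4 deaths.

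| Deaths | As written | As named |
|---|---|---|
| 2 | 100 × 0 / 26.06 = 0 | 100 × 2 / 26.06 = 7.7 |
| 3 | 0 | 100 × 3 / 26.06 = 11.5 |
| 4 | 0 | 100 × 4 / 26.06 = 15.3 |

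**Sensitivity to the denominator**

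The visible text does not define total study duration.

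- Using the protocol's maximum participation of 281 days, which includes up to 42 days of screening, patient-years are 40 × 281/365.25 = 30.77. The named rate is then 6.5 (2 deaths) to 13.0 (4 deaths).
- Going the other way, suppose those who die contribute no follow-up. Then 2 deaths give 100 × 2 / (38 × 0.6516) = 8.1, and 4 deaths give 100 × 4 / (36 × 0.6516) = 17.1.

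With no transplants, the rate as written is 0 in every case.

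**The case against.** **The intent is plain and little is lost.** Death appears in the name of the rate, in the SAP endpoint list, in the protocol and in the time-to-event definition, so a careful programmer would probably ask. Deaths are reported in the all-cause mortality rate, in overall survival and in the composite's own Kaplan-Meier, log-rank and Cox analyses. The trial's primary endpoints are safety endpoints, and the secondary tests carry no multiplicity adjustment. All of this stands, and it limits the severity. It does not make the numerator right.

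**A reader might infer that the meaning of death is left open.** The composite does not state a cause, whereas the SAP writes "overall survival which is defined as the time from start of study treatment to death due to any cause" for survival, and the name could be parsed as death resulting from IPF deterioration. Read together, however, the documents point to death from any cause:

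- Patients without an event are censored no later than the date last known alive, and there is no separate rule for a patient who dies of something else.
- The composite is to be analysed like time to respiratory hospitalisation or death, where only patients who have not died are censored.
- SAP Section 8 adds death to the exacerbation endpoint to avoid dependent censoring, which also fits all-cause death.

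This calls for a clarifying clause and is not a second defect.

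**A reader might also infer that chi-squared tests are unsound here because they ignore person-time.** The size does not support that. Exact calculation with 40 per arm and assumed hazards of 0.1, 0.3 and 0.5 per year gives false-positive rates of 5.3%, 5.2% and 4.9% under equal follow-up. If 30% of one arm stops treatment at Day 71 but is followed for 12 more weeks, the rates are 5.3%, 5.7% and 5.7%. They reach 5.5%, 7.4% and 8.6% only if 30% of one arm and none of the other leave the study at Day 71. Protocol Section 8.4.1 aims to prevent that by following patients who stop treatment. The SAP also already describes the accompanying intervals as intervals for proportions.

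**Conclusion.** The numerator is wrong as written. It omits a component that the rate's name, the protocol, SAP Section 3.2 and the paired time-to-event definition all include. That rests on the text alone and needs no assumption.

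The numerical size is illustrative: 0 against 7.7 to 15.3 per 100 patient-years, assuming 40 subjects with full follow-up to Day 239, no transplants and 2 to 4 deaths in the arm. The documents do not say how many events to expect.

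The severity is minor. The error affects one unadjusted secondary rate and its test. It would be too strong to conclude that the trial fails to report deaths or that the composite as a whole is invalid, because the time-to-event analyses of the same composite include deaths.

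**What to change.** Redefine the numerator in SAP Section 7.5.2.5 along these lines:

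> The number of patients with lung transplantation because of IPF deterioration, or death from any cause, whichever comes first, from the start of study treatment to 12 weeks after its end, each patient counted once.

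Two details matter.

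- **Window.** The numerator as written drops the 12-week limit, and the name attaches it to transplantation only, whereas the time-to-event version stops follow-up of event-free patients at 12 weeks for the whole composite. Adding death without a window would leave open whether a later death counts, so the rate and the time-to-event analysis could still count different deaths.
- **Cause.** One clause confirming death from any cause, used in both the rate and the time-to-event analysis, removes the remaining ambiguity.

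The cost is a few words in the SAP and a matching line in the table specification. No new data are needed and the design does not change. It should be settled before unblinding, so that nobody has to choose between two counts after seeing them.

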#### **8.4. Subject Withdrawal**

##### **8.4.1. Withdrawal Criteria**

Subjects may choose to withdraw from study treatment or the study at any time for any reason. In addition, subjects must have study treatment discontinued for any of the following reasons:

- The subject is unwilling or unable to adhere to the protocol.
- The subject becomes pregnant or begins breastfeeding.
- The subject experiences an SAE, clinically significant AE, severe laboratory abnormality, intercurrent illness, or other medical condition that indicates to the Investigator that continued participation is not in the best interest of the subject.
- 

- Another medical reason, at the discretion of the Investigator and/or the Medical Monitor that indicates continued participation is not in the best interest of the subject.

The only reason for withdrawal from the study should be subject withdrawal of consent to participate.

Subjects who discontinue study treatment should be followed for outcomes as long as they agree to continued participation in the study.

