For SAEs, a Serious Adverse Event Form must also be completed with as much information as possible and submitted in the time frame described below in Section 14.6. When new significant information is obtained as well as when the outcome of an event is known, the Investigator should record the information on a new SAE form. If the subject was hospitalized, a copy of the discharge summary and any other relevant hospital records (eg, admission report, laboratory test results, etc.) must be included as part of the subject medical file.

The clinical course of each AE will be followed until resolution, stabilization, or until it has been determined that the study treatment or participation is not the cause.

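### Time to lung transplantation or death: survivors are cut off at 12 weeks after the end of treatment, but deaths count whenever they are known, so censoring depends on the later outcome

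*SAP*

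**What the plan says.** SAP 7.5.2.5 starts the clock when treatment begins and says of the composite that "deterioration of IPF resulting in lung transplantation (up to 12 weeks after the end of study treatment) or death will be analyzed similarly", with the hospitalization endpoint as the model. The bracketed limit is attached to transplantation; death follows it without one. SAP 3.2 has the same word order.

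For subjects without an event, the date used is the earlier of two: a patient with no known transplantation "or death at the time of analysis will be censored to 12 weeks after the end of study treatment or the last known alive date". Whether a subject has died is judged at the time of analysis, not at the 12-week point.

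Overall survival, in the same SAP section, is handled differently: "Any patient not known to have died at the time of analysis will be censored to the last known alive date". There neither deaths nor survivors are capped.

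The composite inherits the hospitalization methods: a comparison of each active arm with placebo "performed using a log-rank test stratified with standard of care to generate p-value for each comparison", a KM median and plot, event-free proportions at 8-week intervals, and a stratified Cox hazard ratio.

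Neither document defines the end of study treatment for this purpose. Protocol 5.3, 12.4.2 and 14.5 count 12 weeks from the last dose, whereas Protocol 7.1 and 12.3 label Visit 14, two weeks after the last dose, End-of-Treatment.

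**The concern.** Censoring must not depend on what happens to the subject afterwards. Here it does: take two subjects with the same last dose, both followed past the 12-week cap. The one who dies contributes risk time up to death; the one who lives contributes risk time only to the cap. Past a subject's own cap, the only way to remain in the risk set is to die later. The hazard in that stretch is overstated, because the survivors who should be in the denominator have been removed.

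At stake are the KM tail, the median and, in less likely circumstances, the hazard ratio of a listed secondary endpoint that is also repeated in the per-protocol set and in subgroups. With about 40 subjects per arm, a single late death can shape the end of the curve.

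**Working it through.** **1. Where the cap falls.** The documents give no power, event count or hazard ratio for this endpoint, so there is no planned figure to reproduce. The dates come from the visit schedule.
- Cap counted from the last dose, completer: Day 155 + 84 = Day 239, the planned day of Visit 16.
- Cap counted from Visit 14: Day 169 + 84 = Day 253. Visit 16 is at most 70 + 7 = 77 days after Visit 14 or ET, so this cap lies beyond planned follow-up.

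**2. Can deaths past a last-dose cap be known?** Yes, by several routes.
- Visit windows: (14 + 7) + (70 + 7) = 98 days after the last dose, 14 days past the cap.
- COVID-postponed Visit 14 (Protocol 18.6.2.3): 8 weeks, then 10 + 1 weeks to Visit 16, so up to 19 weeks after the last dose.
- COVID early termination: two missed visits (4 weeks), ET 2 ± 1 weeks later, Visit 16 10 ± 1 weeks after that. Nominally 4 + 2 + 10 = 16 weeks, range 14 to 18.
- Protocol 8.4.1: "Subjects who discontinue study treatment should be followed for outcomes as long as they agree to continued participation in the study".
- Protocol 14.5: "The clinical course of each AE will be followed until resolution, stabilization" or a finding that the study is not the cause.
- Vital status known at the analysis.

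**3. Two records on the COVID route.** Last dose Day 29, visits on Days 43 and 57 missed, ET Day 71, Visit 16 Day 141. The cap is 29 + 84 = Day 113.
- Alive at Day 141: censored at Day 113.
- Dies on Day 130: event at Day 130, at risk throughout Days 113 to 130.

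**4. Effect on the curve.** At an event, S(t) = S(t−) × (1 − d/n). If the subject who dies late is the last one at risk, d = n = 1 and S(t) = 0, so a median is reported whatever the true survival.

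**5. How often.** Simulated arms of 40 with exponential mortality, 20% stopping early after 1 to 7 doses, uniform ±7-day visit windows, and the cap at 84 days after the last dose. All of these are assumptions.

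| Deaths known to | KM reaches 0, 10 deaths per 100 patient-years | KM reaches 0, 20 per 100 |
|---|---|---|
| Each subject's own Visit 16 | about 0.6% | about 1.1% |
| 98 days after last dose | about 6% | about 11% |

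If 20% of subjects have COVID-delayed visits and deaths are known to Visit 16, the range is about 4 to 8%.

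The mortality range is a judgement. The median survival of 2.5 to 3.5 years in Protocol 5.1 implies, if exponential, 0.693/3.5 = 0.198 to 0.693/2.5 = 0.277, or about 20 to 28 per 100 patient-years. The entry criteria (FVC and DLco floors, life expectancy of at least 12 months) argue for less. Higher mortality raises the shares.

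The spread of last-dose dates matters too. If every completer is last dosed at exactly week 22, with a 3-year median survival and deaths known to 7 days past Visit 16, a false median near 34.4 weeks appears in 11 to 17% of arms.

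**6. Hazard ratio and event-free proportions.** With deaths known to 7 days past Visit 16 and 60,000 subjects per arm, the hazard ratio was 0.99 for a true 1.0 and 0.50 to 0.51 for a true 0.50. KM at week 32 was about 0.867, equal to the true value. With 10% against 30% early stopping and deaths known to each subject's own Visit 16, deaths per 100 patient-years were 10.1 in one arm and 10.1 to 10.2 in the other, against a true 10.

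**7. Either symmetric rule removes the artefact.** With both capped, the curve is flat at about 0.86 after the cap and no median is reached. With neither capped and deaths known to a later data cut, KM follows the truth (0.835 to 0.838 at week 40, true 0.837).

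**The case against.** The strongest reply is that the protocol's schedule nearly closes the gap. ET and both follow-up visits are tied to the subject's own final dose, and adverse events are collected to 12 weeks after it. A subject who stops at Day 29 has Visit 16 at about Day 113, on the cap, not at Day 239. Trial end is the last subject's last visit, and no survival follow-up is described. If the end of study treatment means Visit 14 or ET, the cap lies past the latest planned Visit 16, on the COVID routes as well, and survivors are in practice censored as for overall survival. The ±7-day window on Visit 13 also spreads completers' caps over Days 232 to 246, so a death on Day 245 need not be the last subject at risk. All of this stands, and it is why the effect is small.

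It does not rescue the rule. The SAP does not say which date is meant, the protocol elsewhere counts 12 weeks from the last dose, and the routes in step 2 can deliver later deaths. The sponsor may have intended the limit to cover death as well, but a programmer following the text would not apply it.

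A reader might also infer that the arm with more early stopping will look worse with no true difference in mortality. Simulated hazard ratios of about 1.10 do arise with 10% against 30% stopping, but only if deaths in early stoppers are known to a common Day 239. Likewise, KM curves falling to zero in 72 to 91% of arms require deaths known to Day 365. The documents schedule neither, so these are extreme scenarios, not expected results.

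**Conclusion.** The rule is wrong as written: deaths are open-ended, survivors are capped, and censoring therefore depends on the future outcome. The date that sets the cap is undefined.

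Under the planned schedule few deaths fall past the cap, the hazard ratio is nearly unbiased, and the event-free proportions up to week 32 are sound. The practical risk, if the cap counts from the last dose, is a KM tail that drops to zero with a false median. This is uncommon when deaths are known only to Visit 16, and reaches roughly one arm in ten under the higher assumed mortality if deaths are known to 98 days after the last dose. These shares rest on assumed mortality, early stopping and visit timing.

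The documents do not support a claim that the hazard ratio is biased in general. With no true effect, that needs both unequal early stopping and deaths known well past each subject's own cap.

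**What to change.** In SAP 7.5.2.5, define the end of study treatment (last dose, or Visit 14/ET) and apply one horizon to deaths, transplants and survivors. Either of two rules works:

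- **Capped:** an event is transplantation due to IPF deterioration, or death, on or before 12 weeks after the defined date. Everyone else, including subjects who die or are transplanted later, is censored at the earlier of that 12-week point and the last known alive date.
- **Uncapped:** drop the 12-week limit for both components and censor event-free subjects at the last known alive date, as for overall survival.

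Carry the same wording to SAP 3.2 and list the change in SAP Section 8. The capped rule keeps the transplantation limit already in the protocol endpoint.

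The cost is a sentence or two before unblinding. Under the capped rule a few late deaths leave this composite, but they remain in overall survival.
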